#### Secondary Objectives:

- 1) Investigate if there is a difference in surgeon assessment of surgical exposure when performing surgery under deep vs. moderate NMB
- 2) Investigate and compare various exploratory endpoints between deep and moderate NMB. These endpoints include: the total dose of analgesics during the procedure, the total dose of analgesics

postoperatively, postoperative shoulder pain, total intraoperative blood loss, operating time, postoperative nausea, time to the first *postoperative* antimetic, total dose of antiemetics postoperatively, and postoperative RASS scores (Richmond Agitation Sedation Scale)

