#### RASS scores:

RASS scores will be assessed and collected verbally by the PACU nurse (Hours 1, 6, and 12 post-

operatively). Hour 24 will be collected by phone call. This data will be captured on the research assessment form (see Appendix 2).

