Analysis of the primary endpoint which involves IAP will be AUCIAP compared between the two arms using the linear mixed-effects model: randomized arm as the fixed-effect, BMI as the adjustment covariate, with surgeon-level random effects. Transformation of the outcome may be applied if the normality-of-errors assumption is violated. As a secondary analysis, the longitudinal IAP measurements will be analyzed using linear mixed-effects models including time and randomized arm as fixed-effects with stratification variable (BMI), and patient-level random effects, nested within surgeons. In the rare case that the patient's IAP is beyond 15 the surgeon will be unblinded to the IAP, and only the IAP up to the point of unblinding will be included in the analysis. 15 is the conventional goal for the upper limit of IAP at MSKCC. Investigators request they know the IAP at a level of 15, so they can weigh risk/benefit of continuing to operate at that higher threshold of IAP. In this rare occurrence, patients will still be included in the analyses as modified intent-to-treat, including IAP values until IAP-unblinding.

Analysis of the second primary endpoint will be AUCpain within 6-hours postoperation. AUCPain analysis will be conducted with linear mixed-effect model with appropriate transformation for the outcome for normality. The model will include randomized arm as fixed-effects along with stratification variable (BMI), and patient-level random effects, nested within surgeons.

For the primary analyses, all recorded IAP will be analyzed in a modified intent-to-treat fashion. Where a patient randomized to moderate NMB crosses over to deep NMB, all recorded IAP will be analyzed under the randomized arm. As a secondary analysis of the primary outcome, we will perform an as-treated analysis where the set of IAP values will be assigned to the actual intervention received. Correlation between AUCIAP and AUCPain will be summarized using Spearman correlation coefficient. Additionally, the primary endpoints will be summarized between patients with and without neuromonitoring issues (see

Section 13.0). As a sensitivity analysis, planned analyses of both primary endpoints will be repeated after excluding patients with neuromonitoring issues (see Section 13.0).

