Although the occurrence will probably be rare, accidental unblinding will be recorded as a protocol violation as part of standard reporting procedure. According to the ICH E9 Statistical Principles for Clinical Trials, usually of violations that occur post-randomization, it is appropriate to include the data from such subjects in the analysis, consistent with the modified intention-to-treat principle. We will include these cases in the primary analysis of the primary outcome in the randomized arm. For each case of major protocol violation, we will enroll an additional patient randomized and included in the analyses. Also, we will perform per protocol analysis that excludes patients who had accidental unblinding.

Surgeon assessment of surgical conditions (continuous measure, on a 1 to 5 scale) recorded every 30 minutes, will be analyzed with linear mixed-effects models as above.

Estimated blood loss (EBL) will be compared between the two arms using linear mixed-effects model (randomized arm and BMI fixed-effects variables, and surgeon-level random effect), accounting for duration of surgery if necessary (i.e., rate of EBL). Transformation of the outcome may be applied if the normality-of-errors assumption is violated.

Postoperative pain (surgical and shoulder pain, 0 no pain to 10 worst pain imaginable), defined at postoperative 1-hour, 6-hour, 12-hour, 24-hour, and 48-hour post operation will be compared between the two arms using linear mixed-effects models with appropriate transformation for the outcomes for normality.

The model will include patient-level random effects (nested within surgeons), treatment arm, and time as fixedeffects, along with stratification variable (BMI) as adjustment factors. To address potential confounding due to history of chronic pain, patients with chronic pain will be excluded from protocol. Chronic pain will be defined as a patient on a sustained-release opioid in the last 3 months. Besides patient-reported pain scores, perioperative analgesia use will be analyzed similarly to the pain scores: intraoperative cumulative IV analgesia use will be compared between the two arms after adjusting for duration of surgery; while postoperative IV analgesia use will be analyzed as cumulative total dose within the first 6-hours post surgery and until prior to discharge (with adjustment for duration of postoperative stay in the analysis).

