Postoperative nausea (measured at the same intervals) will also be analyzed with linear mixed-effects models. To address potential confounding due to preoperative risk for nausea, the model will include adjustment for preoperative Apfel score (4 point scale with a maximum of 3 points due to an all male patient population) and preoperative EMEND use. In addition to patient-reported nausea scores, postoperative antiemetic use will be analyzed in the following fashion: the use of any antiemetics will be analyzed with a mixed-effects logistic regression model, and the use of any antiemetics within the first 6-hours post surgery and until prior to discharge will be analyzed with linear mixed-effects models. Time to first rescue antiemetic medication will also be recorded and compared between the two arms using Kaplan-Meier approach and log-rank test.

We will assess the relationship between the treatment arms and operating time (defined as the time between incision to surgery end) using a linear mixed-effects model with transformation for the outcome for normality. The model will include treatment arm and stratification variable (BMI) and surgeon-level random effect

Richmond Agitation Sedation Scale (RASS) scores, measured at 1, 6, 12, 24 hours postperatively will be modeled and compared between the two arms using linear mixed-effects model. The model will include treatment arm and stratification variable (BMI) and surgeon-level random effect.

One primary concern from deep paralysis is postoperative pulmonary complications and the need for reintubation and prolonged postoperative intubation. All patients who receive neuromuscular blockade are at 23

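### The exploratory RASS model lists neither a patient effect nor a time term, so fitted as listed to four scores per patient its standard error is not valid in general

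*Combined protocol and SAP*

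**What the plan says.** RASS is among the exploratory endpoints in Section 2.0 (Secondary Objectives). Sections 4.1 and 12.0 have it collected four times per patient: at hours 1, 6 and 12 by the PACU nurse and at hour 24 by telephone.

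Section 14.0 then says: "Richmond Agitation Sedation Scale (RASS) scores, measured at 1, 6, 12, 24 hours postperatively will be modeled and compared between the two arms", using a linear mixed-effects model. The terms follow: "The model will include treatment arm and stratification variable (BMI) and surgeon-level random effect". The paragraph just before it gives the same terms to a single-value outcome: "We will assess the relationship between the treatment arms and operating time (defined as the time between incision to surgery end".

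Other repeated outcomes in Section 14.0 are handled differently:

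- Pain at 1 to 48 hours: "The model will include patient-level random effects (nested within surgeons), treatment arm, and time as fixedeffects, along with stratification variable (BMI) as adjustment factors".
- IAP, secondary analysis: "the longitudinal IAP measurements will be analyzed using linear mixed-effects models including time and randomized arm as fixed-effects", with BMI and a patient effect nested in surgeon.
- Surgeon-rated exposure (Leiden scale): "recorded every 30 minutes, will be analyzed with linear mixed-effects models as above".

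The RASS text has its own list of terms and no such reference back. Nowhere do the documents say that RASS is reduced to one value per patient, modelled separately at each hour, or given a robust or repeated-measures covariance.

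**The concern.** Four scores from one patient are not four independent observations. A model with only a surgeon effect treats them as independent once surgeon is accounted for. It therefore overstates the information on the arm difference whenever scores from the same patient are positively correlated.

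The missing time term acts the other way. If mean RASS changes between hour 1 and hour 24, that change goes into the residual variance and inflates the standard error. The two errors cancel only by coincidence.

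At stake is the p-value and interval for a between-arm comparison that the plan commits to make, and for which Section 2.0 states a hypothesis of improvement.

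**Working it through.** **Inputs from the documents.** Four scores per patient and the listed model terms (Section 14.0); 1:1 allocation and 120 evaluable patients for each primary endpoint (Section 14.0). No sample size, power or alpha is given for RASS, so there is no plan figure to reproduce.

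**Inputs assumed.** A two-sided 5% test; within-patient correlation rho; tau, the variance of the four time-point means divided by the average variance of scores at a given time; the pattern of standard deviations (SDs) over time.

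**Formula.** Let S be the 4×4 within-patient covariance matrix, v the average of its four variances, and n the patients per arm. With complete data and arms balanced within surgeon:

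- The listed model takes the variance of the arm difference as 2·v(1+tau)/(4n).
- The correct variance is that of a difference in patient means, 2·sum(S)/(16n).
- (listed SE / correct SE)² = 4·v·(1+tau)/sum(S). The sample size drops out.
- With equal variances and constant rho this becomes (1+tau)/(1+3·rho).
- Type I error = 2·(1 − Φ(1.96 × SE ratio)).

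**Worked cases, rho = 0.3.**

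- Equal SDs, tau = 0: 1/1.9 = 0.526; SE ratio 0.725; type I error 15.5%.
- SDs 1, 0.5, 0.25, 0.25, tau = 0: 4v = 1.375; sum(S) = 1.375 + 0.3 × (4 − 1.375) = 2.1625; squared ratio 0.636; type I error 11.8%.
- Equal SDs, AR(1), tau = 0: sum(S) = 4 + 2 × (0.9 + 0.18 + 0.027) = 6.214; squared ratio 0.644; type I error 11.6%.
- Equal SDs, constant rho, tau = 2: 3/1.9 = 1.579; SE ratio 1.26, so the SE is 26% too large; type I error 1.4%. An effect with 80% power under the correct SE has Φ(1.96 + 0.84 − 1.96 × 1.257) ≈ 63%.

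**Type I error of the listed model, nominal 5%.**

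| Within-patient covariance | tau | rho 0.3 | rho 0.5 | rho 0.7 |
|---|---|---|---|---|
| Equal SDs, constant rho | 0 | 15.5% | 21.5% | 26.6% |
| Equal SDs, constant rho | 1 | 4.4% | 8.0% | 11.5% |
| Equal SDs, constant rho | 2 | 1.4% | 3.2% | 5.4% |
| SDs 1, 0.5, 0.25, 0.25, constant rho | 0 | 11.8% | 16.1% | 20.0% |
| SDs 1, 0.5, 0.25, 0.25, constant rho | 1 | 2.7% | 4.7% | 7.0% |
| Equal SDs, AR(1) | 0 | 11.6% | 17.2% | 23.4% |
| Equal SDs, AR(1) | 1 | 2.6% | 5.4% | 9.2% |

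With equal SDs and constant rho the two errors cancel at tau = 3·rho, that is 0.9, 1.5 and 2.1 for the three columns.

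**Simulation.** REML mixed models, 1,000 runs per setting, 120 patients, 6 surgeons (assumed), 10% of hour-24 scores missing at random (assumed). The comparator has patient and time terms, with surgeons entered as blocks. The Monte Carlo error near 5% is about 0.7 percentage points.

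| Setting | Listed model | With patient and time terms |
|---|---|---|
| Constant rho 0.3, tau 0 | 14.4% | 5.0% |
| Constant rho 0.5, tau 0 | 20.3% | 4.5% |
| Constant rho 0.7, tau 0 | 24.6% | 4.6% |
| Constant rho 0.3, tau 2 | 1.9% | 5.0% |
| Constant rho 0.5, tau 2 | 3.5% | 4.5% |
| Unequal SDs, rho 0.5, tau 0 | 14.8% | 5.3% |
| Unequal SDs, rho 0.5, tau 1 | 4.8% | 5.3% |
| AR(1) 0.5, tau 0 | 16.3% | 5.1% |

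A separate simulation with complete data and rho = 0.2 (400 runs per setting) showed both directions. With no trend, the model SE averaged 0.091 against an actual SD of the estimate of 0.120, with 12.3% rejections. With a strong trend the figures were 0.145 against 0.113, with 0.8% rejections.

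**The case against.** The strongest objection is that the text does not settle how the four scores are used. If each hour were analysed separately, arm, BMI and surgeon would be the right terms. That is true, and the finding is conditional on fitting all four scores together. But the plan nowhere says separate analyses, and it speaks of one model.

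Second, the lists of terms in Section 14.0 are not always complete or exact. The nausea paragraph names adjustment variables without mentioning arm. The pain AUC, one value per patient, is given a patient-level effect. The RASS wording may be a slip carried over from the operating-time paragraph, and an analyst might add the missing terms unprompted. That is plausible, but a pre-specified model should not depend on it. The plan spells these terms out for pain and IAP, so leaving them out here can be read as intended.

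Third, every rho, tau and SD above is assumed, and several middle cases land close to 5%. This stands: neither the direction nor the size of the error can be shown for this trial.

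Fourth, the simulated comparator entered surgeons as blocks rather than as a random nesting level, so it is close to the recommended model but not identical. The difference is probably immaterial.

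Finally, RASS is one of several exploratory endpoints and carries no alpha or decision rule. This limits the importance of the point but does not make the stated model right.

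**Conclusion.** The concern holds. Fitted as listed to four scores per patient, the RASS model gives a standard error that is correct only when the two errors happen to cancel, or when there is neither correlation nor change over time. In the cases tabulated, a nominal 5% test runs from about 1% to about 27%; these figures are illustrative and rest on assumed inputs. The arm estimate is not biased when data are complete. The consequence is confined to the RASS p-value and confidence interval: both primary endpoints, the futility look and the pulmonary safety pause are untouched. The model should be corrected before the analysis is run, so that the choice is not made after seeing which version is more favourable.

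**What to change.** Replace the sentence listing the RASS model terms with the structure used for repeated pain scores: arm, BMI stratum and time (as categories) as fixed effects, and a random intercept for each patient nested in surgeon. If separate analyses at each hour, or one summary per patient, were intended, the plan should say that instead; the present terms would then suffice.

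The cost is one sentence in Section 14.0 and no new data. RASS intervals may become wider or narrower.

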risk of residual paralysis at the conclusion of surgery. Patients who experience residual paralysis from inadequate neuromuscular blockade may experience postoperative pulmonary complications such as respiratory distress, aspiration, and pneumonia, ultimately requiring reintubation and prolonged postoperative intubation. The likelihood of respiratory complications and risk for reintubation are not expected to be different between the two arms. *This risk is independent of the dose or timing of rocuronium administration.*NSQIP data reported 0.82% respiratory complications and 0.47 pulmonary emboli/DVT for 1.29% complication risk from postoperative pulmonary complications. If one or more patients requires reintubation, experiences respiratory distress, aspiration or pneumonia among the first 45 elligible patients (≥2.2% incidence rate) regardless of treatment arm, the trial will be paused for the investigators to assess whether the complication was attributable to the intervention prior to restarting the trial. The incidence of 30-day postoperative pulmonary complications will be recorded and summarized by treatment arm. Postoperative pulmonary complications for recording are defined as the need for reintubation, respiratory distress, aspiration, and pneumonia.

For descriptive purposes, we will assess and the accuracy of surgeon's best guess as to which arm a given patient was assigned. This will allow us to assess blinding success. Similarly, all requests by surgeon to change IAP intraoperatively will be recorded and summarized separately by arm using descriptive statistics.

Reintubations will be limited to any intubation that occurs within the first 24 hours postoperatively.

Respiratory distress is defined by tachypnea to a respiratory rate greater than 30, OR desaturation of 10% or greater from baseline spO2. (either criterion alone will satisfy definition)

Aspiration is defined by pharyngeal or gastric contents below the vocal cords. This must be confirmed by suctioning of pharyngeal or gastric contents from the trachea, fiberoptic bronchoscopy or the finding of a new infiltrate on CXR within 24 hours postop.

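### Section 14.0 names prolonged postoperative intubation as a primary concern of deep paralysis but omits it from both the pause rule and the definition of recorded pulmonary complications

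*Combined protocol and SAP*

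**What the plan says.** Section 14.0 introduces its respiratory safety monitoring with this sentence: "One primary concern from deep paralysis is postoperative pulmonary complications and the need for reintubation and prolonged postoperative intubation". It then describes what residual paralysis may lead to and closes the description with the same pair of airway outcomes: "ultimately requiring reintubation and prolonged postoperative intubation".

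Two operative statements follow in the same section.

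- **Pause rule.** The trial is paused for an attribution review, whichever arm the patient is in, on this condition: "If one or more patients requires reintubation, experiences respiratory distress, aspiration or pneumonia among the first 45 elligible patients".
- **Recording definition.** The 30-day incidence is to be summarized by arm, and its content is fixed as follows: "Postoperative pulmonary complications for recording are defined as the need for reintubation, respiratory distress, aspiration, and pneumonia".

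Two of the supporting definitions matter here. The one for reintubation reads: "Reintubations will be limited to any intubation that occurs within the first 24 hours postoperatively". The one for distress asks for a breathing rate above 30 or a fall in oxygen saturation of at least 10% from the patient's baseline, and either is enough. Aspiration needs confirmation by suctioning, bronchoscopy or a new infiltrate. Prolonged postoperative intubation is not defined anywhere, and neither it nor extubation time appears under Data to Be Collected in Section 16.0.

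**The concern.** The section names two airway outcomes of residual paralysis and carries only one of them into the rules meant to detect it. A tube that was never removed is not an intubation occurring after surgery, so it does not meet the reintubation definition. Nor does it by itself satisfy the criteria for respiratory distress, aspiration or pneumonia.

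The pause rule is the plan's only pre-set safety trigger, and the 30-day pulmonary summary is the only by-arm safety summary in Section 14.0. Both could show no event while one of the two named airway outcomes had occurred. A reader of the final report would take the pulmonary summary as covering the concern that the section states, and for this outcome it would not.

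**Working it through.** **1. Compare the stated concern with the two lists (all Section 14.0).**

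| Event | Named as a concern | Pause rule | Recording definition |
|---|---|---|---|
| Reintubation | yes, twice | yes | yes |
| Prolonged postoperative intubation | yes, twice | no | no |
| Respiratory distress | yes | yes | yes |
| Aspiration | yes | yes | yes |
| Pneumonia | yes | yes | yes |

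Prolonged intubation is the only specific event named in the rationale that appears in neither list.

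**2. Reproduce the plan's own figures.**

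- Pause threshold: 1/45 = 2.22%, which agrees with the stated 2.2%.
- Background rate: 0.82% + 0.47% = 1.29%, which agrees with the stated figure ("for 1.29% complication risk from postoperative pulmonary complications").

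**3. Chance of a pause under the current list.** With independent patients and event probability p, the chance of at least one event in 45 is 1 − (1 − p)^45. At p = 0.0129 this is 1 − 0.9871^45 = 44.2%. The 1.29% includes deep vein thrombosis and pulmonary embolism, which are not on the list, so it is only a stand-in for the rate of listed events. At 0.82% the chance is 31.0%, and at 0.47% it is 19.1%.

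**4. Effect of adding the omitted event.** The documents give no rate for prolonged intubation. Let q be an assumed proportion of patients who have it and no other listed event. The two groups do not overlap, so the chance of a pause becomes 1 − (1 − 0.0129 − q)^45. The expected number left uncounted among 130 randomized patients is 130 × q.

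| Assumed q | Chance of a pause with the event added | Expected uncounted among 130 as written |
|---|---|---|
| 0 | 44.2% | 0 |
| 0.1% | 46.7% | 0.13 |
| 0.25% | 50.3% | 0.33 |
| 0.5% | 55.6% | 0.65 |
| 1.0% | 64.7% | 1.3 |

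The threshold of one event in 45 is unchanged. Under the present wording these patients add nothing to the trigger at any value of q.

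**The case against.** **Other reporting would catch the patient.** This is largely right as far as it goes. Section 11.0 provides for CTCAE and Clavien-Dindo recording. Section 16.0 lists complications of Grade 3 or greater and length of stay. Section 17.0 requires disclosure of adverse events to the IRB, and Section 17.2 requires serious adverse event reporting for 30 days. The patient might also meet the desaturation, aspiration or pneumonia criteria. A reader might infer that he is never counted; the documents do not support that. What remains is that none of the general routes feeds the 45-patient rule or the by-arm pulmonary summary.

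**Prolonged intubation is downstream of events already listed.** Section 14.0 can be read as saying that distress, aspiration and pneumonia lead to it, so that counting those is enough. But reintubation stands in the same downstream clause and is still listed separately in both places. The reading does not explain why one was kept and the other dropped.

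**The risk is the same in both arms.** Section 3.4 says that with sugammadex the risk of residual weakness is equal for deep and moderate block. Section 14.0 says the risk does not depend on rocuronium dose or timing. A reader might infer that the omission favours the deep arm; the documents give no basis for that. The wait required by Section 4.1 when the post-tetanic count is below 1 does not supply one. It is a wait before reversal, of unstated length, and is not the same as prolonged postoperative intubation.

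**Nothing is tested.** This is correct. The plan promises a descriptive summary by arm, so no planned comparison or no-difference conclusion is compromised.

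**Conclusion.** The mismatch is certain on the text: Section 14.0 twice names prolonged postoperative intubation beside reintubation, and neither the pause rule nor the recording definition includes it. The consequence is limited. A patient not extubated at the end of surgery who meets no other listed criterion is not counted, on that ground alone, in those two places.

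The expected numbers are small, at most 1.3 patients of 130 over the range tried. That range is an assumption, not a figure from the documents, and the pause probabilities also assume independent patients and the 1.29% background rate. The point still matters for a rule that a single event triggers. No primary endpoint, power or sample-size figure depends on it.

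**What to change.** Reconcile the stated concern with the two lists in Section 14.0: add prolonged postoperative intubation to both the pause rule and the recording definition, with an operational definition chosen by the investigators. Add extubation time to Data to Be Collected in Section 16.0. The documents do not say that this time is in the electronic record. However, the nausea schedule in Sections 4.1 and 12.0 already times an assessment from extubation, so the study appears to rely on knowing it. If the omission is deliberate, Section 14.0 should give the reason.

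The cost is a phrase in two sentences, one definition and one data field. There may also be an extra pause for a patient kept intubated for an unrelated reason. The attribution review already required at a pause would resolve such a case.

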#### 9.0 TREATMENT/INTERVENTION PLAN

[figure not shown]
A total of 130 patients scheduled for robotic prostatectomies will be randomized into two groups: deep (experimental intervention group) versus moderate (control) blockade, with 120 expected to be evaluable for each of the two primary endpoints. In both groups, anesthesia will be induced and maintained per our department's current routine, and standardization will is clearly defined previously in the protocol. For each patient in either arm of the study, recovery from induction dose of rocuronium will be established before reinitiating muscle blockade (deep versus moderate) with rocuronium infusion. Level of the blockade will be monitored continuously with GE Anandic NMT device and dose of rocuronium will be titrated.

All patients will be maintained in the same surgical position (angle of Trendelenburg) per robotic urological surgery standard. All surgeons will be blinded to the 'starting IAP' value and the IAP value will be recorded at 15-minute intervals. Changes in IAP outside the 15-minute interval measurement point will also be recorded. Increases or decreases in IAP per surgeon's request will be allowed throughout the case. Surgical exposure/visualization will be assessed at 30-minute intervals using the Leiden surgical rating scale of 1 to 5. Surgeons will be alerted if IAP reaches 15, which is the standard upper limit of IAP at MSKCC. Investigators request they know the IAP at a level of 15, so they can weigh risk/benefit of continuing to operate at that higher threshold of IAP. At the end of a case, patients in both arms will be reversed with sugammadex at fascia closure. Data will be collected from the of the surgical case. Patients who experience unexpected intraoperative events including death, conversion to open procedure, a decline in clinical condition that would end a planned procedure, anaphylaxis, or a life-threatening hypersensitivity reaction to any medication will be removed from the study.

Estimated blood loss will be recorded from Electronic Medical Record. Postoperatively, endpoints (pain and nausea) will be recorded on all patients by a PACU nurse and research staff(up to 48 hours postoperatively) according to pain and nausea scales as described above. The a PACU nurse will perform these assessments while the patient is on-site. The research nurse will complete 24 and 48-hour assessments by telephone.

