#### 17.2 Serious Adverse Event (SAE) Reporting

An adverse event is considered serious if it results in ANY of the following outcomes:

- Death
- A life threatening adverse event
- An adverse event that results in inpatient hospitalization or prolongation of existing hospitalization
- A persistent or significant incapacity or substantial disruption of the ability to conduct normal life functions
- A congenital anomaly/birth defect
- Important Medical Events (IME) that may not result in death, be life threatening, or require hospitalization
  may be considered serious when, based upon medical judgment, they may jeopardize the patient or subject
  and may require medical or surgical intervention to prevent one of the outcomes listed in this definition

Note: Hospital admission for a planned procedure/disease treatment is not considered an SAE.

SAE reporting is required as soon as the participant starts investigational treatment/intervention. SAE reporting is required for 30-days after the participant's last investigational treatment or intervention. Any events that occur after the 30-day period that is unexpected and at least possibly related to protocol treatment must be reported.

Please note: Any SAE that occurs prior to the start of investigational treatment/intervention and is related to a screening test or procedure (i.e., a screening biopsy) must be reported.

All SAEs must be submitted in PIMS. If an SAE requires submission to the HRPP office per IRB SOP RR-408 'Reporting of Serious Adverse Events', the SAE report must be submitted within 5 calendar days of the event.

The report should contain the following information:

- The date the adverse event occurred
- The adverse event
- The grade of the event
- Relationship of the adverse event to the treatment(s)
- If the AE was expected

- · Detailed text that includes the following
  - o A explanation of how the AE was handled
  - A description of the subject's condition
  - o Indication if the subject remains on the study
- If an amendment will need to be made to the protocol and/or consent form
- If the SAE is an Unanticipated Problem

The PI's signature and the date it was signed are required on the completed report.

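### The 30-day pulmonary complication summary mixes component windows: reintubation counts only to 24 hours, and after the 48-hour call only passive capture is described

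*Combined protocol and SAP*

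**What the plan says.** Section 14.0 sets the outcome and its window: "The incidence of 30-day postoperative pulmonary complications will be recorded and summarized by treatment arm". It then lists the components: "Postoperative pulmonary complications for recording are defined as the need for reintubation, respiratory distress, aspiration, and pneumonia". The definitions that follow carry different time limits.

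- **Reintubation:** "Reintubations will be limited to any intubation that occurs within the first 24 hours postoperatively".
- **Aspiration:** material below the vocal cords, confirmed by suctioning, by bronchoscopy, or by "the finding of a new infiltrate on CXR within 24 hours postop". The 24-hour phrase attaches most naturally to the X-ray route alone.
- **Respiratory distress:** "defined by tachypnea to a respiratory rate greater than 30, OR desaturation of 10% or greater from baseline spO2". No time limit is given.
- **Pneumonia:** no time limit and no definition.

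The same event types drive the pause rule, under which one or more events in the first 45 patients pauses the trial for review.

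On follow-up, Section 9.0 says that "endpoints (pain and nausea) will be recorded on all patients by a PACU nurse and research staff(up to 48 hours postoperatively"). Section 4.1 expects most patients to be discharged before 24 hours. The 24- and 48-hour contacts are then telephone calls, with an 8-hour window either side for the pain scores. They cover pain and nausea, plus RASS at 24 hours.

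For later events, Section 17.2 says that "SAE reporting is required for 30-days after the participant's last investigational treatment or intervention". Section 11.0 plans CTCAE and Clavien-Dindo recording, and Section 16.0 lists grade 3 or greater complications and has the coordinator attend weekly and monthly complication meetings.

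**The concern.** One rate with one 30-day label is built from parts observed over different periods. Nothing in Section 14.0 restricts the 24-hour reintubation limit to the pause rule, and it stands alongside a definition written for recording. Following the plan exactly, a reintubation on day 3 lies inside the stated window but is not counted as a reintubation.

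Ascertainment adds a second difficulty. Respiratory distress depends on respiratory rate and oxygen saturation, which a telephone call does not measure. The text describes no visit, call or chart check for this outcome after 48 hours. SAE reports go into one system (PIMS) and study data into another (REDCap), and no sentence links them for this summary.

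Section 14.0 names pulmonary complications and reintubation as a primary concern with deep paralysis. A late reintubation could therefore appear in the SAE file and be absent from the reintubation count in the 30-day table, and readers of the results could take that table as complete to day 30.

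**Working it through.** **1. The plan's own figures.** Section 14.0 gives a reference risk of 0.82% + 0.47% = 1.29% and a pause threshold of 1/45 = 2.2%. Both reproduce, and neither depends on the window question. Two cautions apply to the 1.29%. It includes DVT and pulmonary embolism, which are outside this outcome. Section 3.5 also attaches the two percentages to the opposite labels (respiratory 0.47%, DVT or PE 0.82%). The sum is unaffected, but the labels should be reconciled.

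**2. Windows side by side.**

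| Component | Limit in Section 14.0 | Agrees with the 30-day label? |
|---|---|---|
| Reintubation | 24 hours | No |
| Aspiration, X-ray route | 24 hours | No |
| Aspiration, suction or bronchoscopy | none | Yes |
| Respiratory distress | none, but needs bedside measurement | In wording only |
| Pneumonia | none, undefined | Yes |

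**3. How much one event weighs.** Planned enrolment is 130, or 65 per arm. Expected events = number of patients × rate.

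- At 1.29%: 130 × 0.0129 = 1.7 in all, and 65 × 0.0129 = 0.8 per arm.
- At 0.82%: 130 × 0.0082 = 1.1 in all, and 65 × 0.0082 = 0.5 per arm.
- At 0.47%: 130 × 0.0047 = 0.6 in all, and 65 × 0.0047 = 0.3 per arm.

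One event in 65 is 1/65 = 1.5%, so missing it moves that arm from 1.5% to 0%.

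**4. What incomplete late capture could do.** The documents give neither the share *f* of 30-day events that occur by 48 hours nor the share *c* of later events that are captured. Both are assumed below, and 1.29% is treated as a true 30-day rate for illustration. Recorded rate = 1.29% × (f + (1 − f) × c).

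| f | c = 0 | c = 50% | c = 90% |
|---|---|---|---|
| 25% | 0.32% | 0.81% | 1.19% |
| 50% | 0.65% | 0.97% | 1.23% |
| 75% | 0.97% | 1.13% | 1.26% |

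The result runs from about a quarter of the true rate to almost all of it, depending on two unknown inputs. The table concerns missed ascertainment only. The separate effect of the 24-hour reintubation rule cannot be sized, because the documents do not say how many late reintubations would also qualify under another component.

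**The case against.** The strongest defence has four parts.

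- **The 24-hour limit has a purpose.** Section 14.0 frames the worry as residual paralysis, and an early window isolates reintubations plausibly due to it. Counting every intubation to day 30 would bring in unrelated ones, for example for reoperation. This stands as a reason to keep a 24-hour measure, but not as a reason to report it under a 30-day label.
- **The patient may still be counted.** Someone reintubated on day 10 for pneumonia counts as pneumonia, and respiratory failure would often meet the distress criteria. This stands for the overall incidence in many cases. It does not repair the reintubation component.
- **There are routes for late events.** The 30-day SAE rule covers death, life-threatening events and hospitalization, so a serious late event should be reported. The complication recording and meetings add to this. This stands, but these routes are passive, those in Sections 11.0 and 16.0 state no window, and none is tied to this summary.
- **The outcome is descriptive.** No test, power or alpha rests on it, and with fewer than one expected event per arm no by-arm safety claim could be supported even with perfect capture. This stands and limits the importance of the point.

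A reader might go further and infer that the reported figure is really a one-to-two-day rate, since 24/720 hours is 3.3% of the window and (48 + 8)/720 hours is 7.8%. The documents do not support that. Those are shares of calendar time, not of events. Two components have no time limit, and serious late events have a reporting route. The inference would need later capture to be close to zero.

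**Conclusion.** The concern holds as a conflict between a stated rule and a stated outcome. The 30-day incidence combines components with mixed windows, and collection from 48 hours to day 30 is passive and not specified for this outcome. A reintubation after 24 hours is excluded as a reintubation, though not necessarily as a pulmonary complication. Milder late events and events treated at other hospitals are the ones most likely to be missed.

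The undercount cannot be computed from the documents. What can be said is that expected counts are so low, about 0.8 per arm at 1.29% and fewer at the respiratory-only rates, that a single missed event changes an arm's summary. The conclusion assumes that the 24-hour reintubation limit applies wherever reintubation is used, as the text reads. It also assumes that no later check is scheduled in the appendices, which appear only by title, or in Section 10.0, which shows no content.

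**What to change.** In Section 14.0, choose one of two wordings. Either state that the 24-hour limits on reintubation and on the X-ray finding apply to the pause rule only, and count reintubation, aspiration and pneumonia to day 30 in the summary. Or report reintubation separately as a 24-hour component and take it out from under the 30-day label.

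In both cases:

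- label respiratory distress as an in-hospital measure;
- add a definition of pneumonia;
- fill the summary from an electronic record check at day 30, reconciled with the SAE reports already required to that day;
- list late intubations unrelated to residual block, such as those for reoperation, separately.

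The cost is protocol wording and 130 record checks by the existing coordinator. Events treated at other hospitals may still be missed, and the report should say so.
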